#### 4.2 SCIENTIFIC RATIONALE FOR STUDY DESIGN

The double blinded randomized clinical trial is the gold standard design with causal implications of the intervention.

#### 4.3 JUSTIFICATION FOR INTERVENTION

The one time perioperative mode of delivery for the intervention is best design and appropriate. Post-surgery patients will complete a worksheet for pain scores and pain medication. Study procedures will remain same for all patients.

#### 4.4 END-OF-STUDY DEFINITION

End-of-study is defined as completing the intervention and any portion of worksheet. Study times are expected to take place during a 2 week time period.

### 5 STUDY POPULATION

#### 5.1 INCLUSION CRITERIA

Patients undergoing laparoscopic inguinal hernia repair at the Mount Sinai Hospital

#### 5.2 EXCLUSION CRITERIA

Patients who are younger than 18 years old, have a history of chronic opiate usage, liver or kidney disease, pain syndromes, allergy to bupivacaine, are pregnant or are unable to independently give consent will be excluded from the study preoperatively.

Pregnant patients will be excluded due to safety of surgery and anesthetics in pregnant patients

#### 5.3 LIFESTYLE CONSIDERATIONS

N/A

#### 5.4 SCREEN FAILURES

Patients who do not receive the intervention or placebo.

#### 5.5 STRATEGIES FOR RECRUITMENT AND RETENTION

100 patients will be recruited at Mount Sinai Hospital who are scheduled to receive a laparoscopic inguinal hernia repair. Patients will be screened by research team members and attending physicians. Recruitment will occur if a patient is interested in the study and they meet the inclusion criteria and do not meet exclusion criteria. Potential patients will receive an explanation of study procedures and expectations. If they would like to participate, they will be consented according to standard procedures. Patients will be discharged with a worksheet that asks for pain levels and pain medication usage after their operation. They will be expected to bring the completed sheet during their post-operation follow up visit. There will be no incentives for participation in the study.

Given that patients will be enrolled in the clinic and the emergency department after presenting with a disease, they may be overwhelmed and may have limited time to process the risks and benefits of enrolling in this trial. To address the increased vulnerability as described above, we will train all persons involved in the consent process in best practices for consenting a patient. Ultimately, the physician will make the decision for enrollment.

## 6 STUDY INTERVENTION(S) OR EXPERIMENTAL MANIPULATION(S)

### 6.1 STUDY INTERVENTION(S) OR EXPERIMENTAL MANIPULATION(S) ADMINISTRATION

#### 6.1.1 STUDY INTERVENTION OR EXPERIMENTAL MANIPULATION DESCRIPTION

The study intervention is 0.25% bupivacaine. This neural block will be administered at the transabdominal plane. Other clinical trials have shown benefit of a neural block for hernia repairs on pain scores. We believe this intervention will work according to similar mechanism.

#### 6.1.2 ADMINISTRATION AND/OR DOSING

Patients are randomized to receive one time administration of either 0.25% bupivacaine or normal saline. The TAP block is done pre-procedure using 0.25% bupivacaine. If patients weigh<100 kg, they will receive a total of 50 mL (25 mL on each side of the abdominal wall). If patients weigh>100 kg, they will receive a total of 60 mL (30mL on each side of the abdominal wall). The TAP plane is identified using ultrasound. All anesthesiologists (not surgeons) working with the attendings involved in this study have been trained in this technique; it is a routine part of their practice. It is anesthesiologists who will be performing the block.

### 6.2 FIDELITY

#### 6.2.1 INTERVENTIONIST TRAINING AND TRACKING

The intervention will be administered at one time point by an anesthesiologist who is trained to administer the medication.

### 6.3 MEASURES TO MINIMIZE BIAS: RANDOMIZATION AND BLINDING

This is a double blinded study. Assignment of the intervention is made prior to the study beginning in pre-numbered envelopes at a 1:1 ratio to optimize power. The data analyst will not be aware of a treatment for any specific patient. Due to the same quantity of the placebo and intervention drug, the treatment should remain indistinguishable with regards to blinding.

### 6.4 STUDY INTERVENTION/EXPERIMENTAL MANIPULATION ADHERENCE

The intervention is completed during the surgery thus no adherence to intervention is required of the patient. The patient will complete a form describing pain score post-surgery and pain medications which will be tracked at the post-operation visit.

## 6.5 CONCOMITANT THERAPY

For this protocol, participants are not restricted to the pain medication they use. Rather, they are to record opioid based and over the counter medication used for pain control.

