## 3 OBJECTIVES AND ENDPOINTS

OBJECTIVES	ENDPOINTS	JUSTIFICATION FOR ENDPOINTS	PUTATIVE MECHANISMS OF ACTION
Primary			
Do TAP blocks improve pain score?	Change in pain score for the intervention versus placebo groups.	Assessing causal effect of TAP block on pain levels through the RCT design is the gold standard approach.	
Secondary			
Do TAP blocks decrease opioid and other pain medication use after surgery?	Assessing number/volume of pain medication.	TAP blocks should directly impact pain medications usage.	
Tertiary/Exploratory			
Does TAP block usage affect complications after surgery?	Assessing complication rate differences between the intervention and placebo groups with regards to complications.	Complications can differ based on treatment. We want to assess if complications rates differ between the two groups.	

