## 4 STUDY DESIGN

### 4.1 OVERALL DESIGN

After receiving approval for the study, we will conduct a prospective single institution randomized clinical trial assessing if using a TAP block perioperatively can reduce pain scores after surgery. Other endpoints include whether there are differences in pain medication usage and complications.

Patients will be screened by research team members and attending surgeons. If the patient is interested, we will consent them for the study after they understand the study details, procedures, and expectations. We will then consent using IRB approved study consent forms and procedures. Patients will undergo a laparoscopic inguinal hernia repair according to standard procedures. Our study will assess if a TAP block impacts pain scores. Patients will be randomized to receive the intervention or placebo. Sequentially numbered sealed opaque envelopes with group allocation inside will alert the anesthesiologist/ surgeon to order Tap block composed of 0.25% bupivacaine or placebo (normal saline).

Inguinal hernia repair will be performed in standard fashion that each individual surgeon is familiar with. No additional tests or blood work outside the standard of care for IHR will be performed for research purposes. In addition, some patients will be given TAP blocks before surgery to help in pain management. In addition, patients will be discharged with a worksheet on which they are to record analgesic use and pain scores on postoperative days one, two, three and four. They are expected to bring the completed log to their two-week follow up visit with their surgeon. Patients may also expect to receive a phone call from a member of the surgical team to remind them to record these metrics.

The TAP block is done pre-procedure using 0.25% bupivacaine. If patients weigh<100 kg, they will receive a total of 50 mL (25 mL on each side of the abdominal wall). If patients weigh>100 kg, they will receive a total of 60 mL (30mL on each side of the abdominal wall). The TAP plane is identified using ultrasound. All anesthesiologists (not surgeons) working with the attendings involved in this study have been trained in this technique; it is a routine part of their practice. It is anesthesiologists who will be performing the block.

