## 9 STATISTICAL CONSIDERATIONS

### 9.1 STATISTICAL HYPOTHESES

- Primary Endpoint(s):

We hypothesize that patients randomized to the intervention will have lower pain scores as compared to the placebo arm.

- Secondary Endpoint(s):

We hypothesize that patients randomized to the intervention will have lower intake of opioid and as compared to the placebo arm.

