### 9.2 SAMPLE SIZE DETERMINATION

Based on previous clinical trials using a pain medication intervention prior to surgery, our sample of 100 will be enough to detect a difference, should one exist. Moreover, the intervention and placebo will be administered randomly with an overall ratio of 1:1 to maximize power for analysis.

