### 9.4 STATISTICAL ANALYSES

#### 9.4.1 GENERAL APPROACH

For descriptive analyses categorical variables will be described using the frequency and proportions. Continuous variables will be described using median and the interquartile range (Q1, Q3). All p-values of statistical tests will be two-tailed with a  $p < 0.05$  considered statistically significant.

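### Opioid use is open to bias from arm-dependent supply: the documents conflict on who knows the arm, and there is no plan to record what patients were given to take home

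*Combined protocol and SAP*

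**What the plan says.** Section 3 defines the secondary endpoint as "Assessing number/volume of pain medication", with no unit or time window. Section 9.1 gives the direction: "We hypothesize that patients randomized to the intervention will have lower intake of opioid and as compared to the placebo arm".

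The described source is the patient's own worksheet, covering postoperative days 1 to 4 and handed in at the two-week visit (4.1). Section 6.5 states "For this protocol, participants are not restricted to the pain medication they use" and has patients record the opioid and over-the-counter medication they used. Section 8.1 says the patient leaves with the worksheet. No section mentions a discharge prescription, its quantity, who writes it, or any record of it.

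On knowledge of the arm, 4.1 says that opening the envelope tells the anesthesiologist or surgeon (the two roles are joined by a slash) whether to order bupivacaine or saline. Sections 4.2 and 6.3 call the trial double blind. Section 6.3 rests this on the equal volume of the two solutions and names only the data analyst as unaware of treatment.

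**The concern.** Opioid intake at home depends on what the patient has as well as on what the patient needs. I assume that take-home opioids come through a prescription, since the documents do not say. A clinician who knew that a patient had received the active block might supply less or none. The worksheet would then show lower intake in the block arm even if the block relieved no pain.

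None of the analyses in 9.4.3, nor the mixed models for opiate consumption in 2.2, uses the amount supplied. A zero from a patient who needed nothing therefore looks the same as a zero from a patient who had nothing. What is at stake is the secondary conclusion that the block lowers opioid intake.

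**Working it through.** **The plan's own figure.** Section 9.2 says of the sample size that "our sample of 100 will be enough to detect a difference, should one exist", but gives no effect size, SD, power or dropout, and nothing for opioid use. The 100 therefore cannot be reproduced. At 1:1 it gives 100/2 = 50 per arm, and 9.4.1 sets two-sided tests at 0.05. For scale, the standardised difference detectable with 80% power is (1.960 + 0.842) × √(2/50) = 0.56.

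**The passages side by side.**

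| Question | What the documents give |
|---|---|
| Who learns the allocation? | 4.1: anesthesiologist or surgeon; 6.3: double blind, only the analyst named |
| Who supplies take-home analgesia? | Not stated |
| Is that person unaware of the arm? | Not stated |
| Is the supply recorded? | Not stated; 6.5 covers medication used |

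The protections that would keep supply independent of the arm are thus either in conflict or absent.

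**Could this matter numerically?** The documents give no inputs on demand or supply, so everything below is assumed apart from 50 per arm and the 0.05 level. In every case the block has no effect. The Mann-Whitney test is used for counts because it is one of the options in 9.4.3, which does not fix the test.

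1. *Some block patients receive no opioid; every placebo patient can obtain one.* Assume that 60% are opioid users, that users take at least one dose and 5 on average, and that block-arm values become 0 with probability f. Two-sided rejection for f = 0, 10, 20, 30 and 40% is about 5, 8, 19, 37 and 62%. At f = 20%, varying the share of users gives 12% (40% users), 19% (60%) and 28% (80%). At f = 20% or more, essentially all rejections favour the block; at f = 0, only about 2.5% do.

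2. *Intake is the smaller of demand and pills supplied.* Demand is negative binomial (dispersion 1), and placebo patients are supplied 12 pills. Two-sided rejection:

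| Block-arm supply | Mean demand 4 | Mean demand 8 | Mean demand 12 |
|---|---|---|---|
| 12 pills (equal) | 4.1% | 4.7% | 4.4% |
| 8 pills | 5% | 22% | 61% |
| 6 pills | 8% | 47% | 87% |
| none for 20% of patients, 12 for the rest | 28% | 32% | 35% |

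3. *Any opioid use, yes or no.* Use equals the share prescribed times the share of those who take it, and 90% of placebo patients are prescribed an opioid. The chance of p < 0.05 favouring the block is Φ{[(p₀ − p₁) − 1.96√(2p̄(1 − p̄)/50)] / √[(p₀(1 − p₀) + p₁(1 − p₁))/50]}, with p̄ the mean of p₀ and p₁. For example, if 50% of those prescribed take it and 70% of block patients are prescribed, p₀ = 0.50 × 0.90 = 0.45 and p₁ = 0.50 × 0.70 = 0.35. The result is Φ[(0.100 − 0.192)/0.0975] = 17%. With 50% to 70% taking what is prescribed, the chance is 7% to 11% if 80% of block patients are prescribed, 17% to 29% if 70%, and 34% to 56% if 60%. These count one direction only, so the comparator is 2.5%.

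With equal supply the error rate is nominal. With a modest difference and low demand it barely moves. With larger differences or higher demand it climbs steeply.

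**The case against.** The strongest reply is that the documents establish neither a supply limit nor an unblinded prescriber.

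- A reader might infer that a discharge prescription caps opioid use. No section mentions one, and the sentence in 6.5 shows only that no restriction is imposed. This stands: the mechanism is a possibility the plan leaves open.
- A reader might infer that the surgeon knows the arm at discharge. The slash in 4.1 leaves open which of the two roles sees the allocation, anesthesiologists perform the block, and 4.2 and 6.3 declare double blinding. This also stands: there is a conflict to resolve, and unblinding is not an established fact.
- A reader might take "Inguinal hernia repair will be performed in standard fashion that each individual surgeon is familiar with" to mean that prescribing follows each surgeon's habit. That sentence concerns the operation.
- A reader might infer that a supply difference could never be detected. Section 10.1.3 says data are obtained by medical record number, with identifiers kept so that further items can be retrieved later, and 6.4 has pain medication tracked at the postoperative visit. Pain scores and over-the-counter use are also collected and might hint at under-supply. The gap is that collection and reporting are not pre-specified.
- Patients left without an opioid equally often in both arms cost sensitivity and leave the comparison valid. The bias needs a supply difference between arms, so it follows in part from the blinding conflict.

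These replies narrow the point without removing it. Even with blinding repaired, the intake result is easier to interpret when the amounts supplied are known.

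**Conclusion.** The point holds as a gap in the plan. The documents conflict on who knows the arm, do not say that the discharge prescriber is unaware of it, and do not plan to record what was supplied. Arm-dependent supply could therefore lower recorded opioid use without analgesia, and the planned data would not tell the two apart.

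The size cannot be known from the documents. Under the assumptions above, two-sided rejection is about 5% for a modest supply difference at low demand and roughly 12% to 35% if 20% of block patients receive no opioid, against a nominal 5% (about 2.5% towards the block). That range is not a ceiling, since more extreme assumptions give more. Nor is it a forecast: the documents do not support saying that such prescribing will occur. The point concerns a secondary endpoint and should be fixed because the remedy is cheap.

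**What to change.** 1. Reconcile 4.1 with 6.3 so that the allocation reaches only the person who prepares the study solution. State that the surgeon and whoever prescribes at discharge remain unaware of it.
2. For every participant, extract from the medical record the opioid prescribed at discharge (drug, strength, units) and any refill up to the two-week visit.
3. Report by arm, beside the intake result, the units prescribed and the number of patients with no opioid prescription.
4. Keep the main intention-to-treat comparison unadjusted for prescribing, which follows randomization. Use the prescribing data only to interpret the result.
5. Add no automatic rule that denies the block credit whenever prescribing differs. A prescriber unaware of the arm may supply less because the patient has less pain, which would be a real consequence of the block, and imbalance can also arise by chance.

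Nothing here changes when or what is prescribed. The cost is a few extra data fields from records the team already uses, and naming who prepares the solution.

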### 6.5.1 RESCUE THERAPY

There will no rescue therapy for this intervention.

## 7 STUDY INTERVENTION/EXPERIMENTAL MANIPULATION DISCONTINUATION AND PARTICIPANT DISCONTINUATION/WITHDRAWAL

### 7.1 DISCONTINUATION OF STUDY INTERVENTION/EXPERIMENTAL MANIPULATION

The intervention will occur at one time point during surgery. There will be no discontinuation after therapy administration.

### 7.2 PARTICIPANT DISCONTINUATION/WITHDRAWAL FROM THE STUDY

Patients may stop participating in the study at any time without penalty. This will not affect their ability to receive medical care at Mount Sinai or to receive any benefits to which they are otherwise entitled. Patients may withdraw permission for the use and disclosure of any protected information for research, but they must do so in writing to the Principal Investigator.

Name: [name]  
Physical Address: The Mount Sinai Hospital Division of General Surgery, [name]  
Mailing Address: [name]  
Academic Office [contact]  
Clinic [contact]

Even if they withdraw permission, the Principal Investigator for the research study may still use the information that was collected if that information is necessary to complete the study. Patients' health information may still be used or shared after they withdraw authorization if they should have an adverse event from participating in the study.

The study doctor, the sponsor or the institution may terminate patients' involvement in this study at any time without the patient's consent. This may be because the study itself has stopped, the instructions of the study team have not been followed, the investigator believes it is in patients' best interest to be

withdrawn, or for any other appropriate reason. If specimens or data have been stored as part of the study, they too can be destroyed without patient consent.

### 7.3 LOST TO FOLLOW-UP

Before being considered lost to follow up, every attempt will be made by the investigator and/or the research team to contact the participant.

## 8 STUDY ASSESSMENTS AND PROCEDURES.

### 8.1 ENDPOINT AND OTHER NON-SAFETY ASSESSMENTS

Study recruitment will include patients who are schedule for a laparoscopic inguinal hernia repair and meet the inclusion criteria but not the exclusion criteria. The screening will be completed by the research team and/or physician. If a patient is interested, they will be approached to consent for the study. If they are still interested and understand the study and its expectations, they will consent using standard consenting procedures. The intervention will be given perioperatively and the procedure will continue according to standard procedures. No deviation from standard care will be made for the inguinal hernia repair. The patient will be discharged with worksheet asking for pain scores and pain medication usage.

### 8.2 SAFETY ASSESSMENTS

As all procedures are according to standard of care, all parts of care will be administered and any complications and events will be tracked.

### 8.3 ADVERSE EVENTS AND SERIOUS ADVERSE EVENTS.

#### 8.3.1 DEFINITION OF ADVERSE EVENTS

Any adverse event as a result of the study intervention. As the intervention in study is a standard of care drug for pain, we do not expect adverse events.

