## 2.3 RISK/BENEFIT ASSESSMENT

### 2.3.1 KNOWN POTENTIAL RISKS

There always exists the potential for loss of private information. There is also always the risk that the TAP block may not provide adequate analgesia.

There is also a risk of bowel perforation during TAP injection. However, this risk is minimal given that the bowel is well visualized with ultrasound guidance and thus avoided at all costs.

All injections of anesthetic carry a <1% risk of local anesthetic systemic toxicity (LAST) which can cause seizures or even cardiac arrest.

As all risks for harm are those included as part of standard treatments, there are no provisions for harm or injury. Any follow-up tests, treatments, or procedures will be performed at cost to the participant.

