### 2.3.3 ASSESSMENT OF POTENTIAL RISKS AND BENEFITS

All physical risks for harm are those included as part of standard treatments, there are no added provisions for harm or injury due to the study. All information will be stored securely and in accordance with IRB policies and expectations. This treatment could prove beneficial to the patient and the larger public in terms of pain control and reducing opioid use.

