#### 8.3.2 DEFINITION OF SERIOUS ADVERSE EVENTS

Serious adverse events as a result of the study intervention will be classified by the attendings. As the intervention in study is a standard of care drug for pain, we do not expect adverse events.

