### 8.3.3.2 RELATIONSHIP TO STUDY INTERVENTION/EXPERIMENTAL MANIPULATION

Adverse events related of the study intervention will be classified as related or not related by the PI and other attendings.

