### 8.3.5 ADVERSE EVENT REPORTING

Adverse events due to study intervention will be reported to IRB.

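### Adverse events are defined and reported only if attributed to the intervention, which contradicts sections 8.2, 8.3.3.2 and 8.3.4 and would weaken any adverse event table by arm

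*Combined protocol and SAP*

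**What the plan says.** All references are to the combined protocol and SAP.

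**Text that makes attribution a condition**
- 8.3.1 defines an adverse event as "Any adverse event as a result of the study intervention".
- 8.3.2: "Serious adverse events as a result of the study intervention will be classified by the attendings".
- 8.3.5: "Adverse events due to study intervention will be reported to IRB". Section 8.3.6 repeats this for serious events.

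**Text that does not**
- 8.2 undertakes to track complications and events of any kind.
- 8.3.3.2 says that adverse events "will be classified as related or not related by the PI and other attendings".
- 8.3.4 has the PI classify relatedness after an event has been notified.
- Sections 3 and 9.4.9 plan a comparison of complications between the arms, with no reference to cause.

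**Related text**
- 9.4.4 (safety analyses) is marked N/A.
- 6.1.1 names the intervention as 0.25% bupivacaine, whereas the synopsis describes it as a TAP block with bupivacaine or saline.
- 4.1: "Sequentially numbered sealed opaque envelopes with group allocation inside will alert the anesthesiologist/ surgeon" to order the assigned injection. Section 6.3 calls the trial double blinded, but the only role it names as unaware of treatment is the data analyst.
- 8.3.1 and 8.3.2 state "we do not expect adverse events", whereas 2.3.1 lists bowel perforation and local anesthetic toxicity with seizures or cardiac arrest.
- 2.3.3: "All physical risks for harm are those included as part of standard treatments".

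**The concern.** An adverse event is normally any untoward event, and its cause is a separate judgement made about it. Here that judgement is part of the definition, so staff cannot follow 8.3.1 and 8.3.3.2 together: an event classed as unrelated is an adverse event under one and not under the other. If 8.3.1 governs, every event judged unrelated leaves the adverse event record and is not reported to the IRB.

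Two things follow for the statistics. An adverse event table by arm would count only part of what happened, which costs sensitivity. If the attributed share differed between arms, the table could also show a difference that is not there or hide one that is. The classifiers are the PI and attendings, and 4.1 leaves open whether some of them learn the allocation.

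The saline arm adds a further gap. On the narrow wording of 6.1.1, an injection injury in a saline patient does not result from the study intervention, so it would be neither an adverse event nor reportable. On the synopsis wording it would be both.

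**Working it through.** **1. The passages side by side.**

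| Question | Sections 8.3.1, 8.3.2, 8.3.5, 8.3.6 | Elsewhere |
|---|---|---|
| Is an unrelated event an adverse event? | No | Yes (8.3.3.2) |
| Which events are picked up? | Those attributed to the intervention | All (8.2) |
| When is cause judged? | As part of the definition | After notification (8.3.4) |
| Do saline-injection harms count? | No if 6.1.1 defines the intervention | Yes if the synopsis does |
| Is there a comparison by arm? | None for adverse events (9.4.4 is N/A) | Complications, unfiltered (3, 9.4.9) |

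The plan is inconsistent. It does not apply attribution first throughout.

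**2. What a causality filter would do.** The plan gives no rates for complications or adverse events overall, and no attribution rates, so there is no figure to reproduce. The inputs from the plan are 100 patients (9.2), 1:1 allocation (9.2, 6.3), hence 50 per arm, and two-sided 5% tests (9.4.1). Everything else below is assumed.

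Let p be the true event rate in an arm and s the share of its events attributed to the intervention. The counted rate is p × s. For counts i and j in n = 50 per arm, with pooled proportion q = (i + j)/100, the Pearson chi-square test rejects when |i − j|/50 ÷ √[q(1 − q) × 2/50] > 1.96. Summing exact binomial probabilities over all such (i, j) gives the rejection rate.

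*No true difference, p = 10%, 20% or 30% in both arms:*

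| Share attributed, bupivacaine / saline | Apparent risk ratio | Rejection at p = 10% | 20% | 30% |
|---|---|---|---|---|
| All events counted | 1.0 | 5.1% | 5.2% | 5.0% |
| 0.5 / 0.5 | 1.0 | 4.3% | 5.1% | 5.5% |
| 0.6 / 0.4 | 1.5 | 6.3% | 10.1% | 14.1% |
| 0.7 / 0.3 | 2.33 | 12.9% | 26.7% | 41.1% |
| 0.8 / 0.2 | 4.0 | 25.6% | 53.9% | 76.0% |

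For example, at p = 20% and shares 0.7 / 0.3, the counted rates are 14% and 6%, a ratio of 2.33.

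*A true difference, with half the events counted in each arm:*

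| True rates | Power, all events | Power, half counted |
|---|---|---|
| 30% v 10% | 73% | 39% |
| 20% v 5% | 66% | 33% |
| 20% v 10% | 30% | 15% |

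An equal filter therefore leaves the false positive rate near 5% and roughly halves power. A false difference needs shares that differ by arm.

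**3. Rare harms.** Section 2.3.1 puts local anesthetic toxicity below 1%, so fewer than 50 × 0.01 = 0.5 cases are expected in the bupivacaine arm. No test would be informative there. For such events the value lies in complete recording and reporting.

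**The case against.** The strongest reply is that the plan does not depend on 8.3.1. Section 8.2 tracks everything, 8.3.4 places notification before the judgement of cause, and the only harms comparison planned, in 9.4.9, has no causality filter. The reports to the IRB are not the analysis data set. This largely stands, and it rules out two stronger readings that a reader might infer:

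- **That cause is always judged before an event is recorded.** Sections 8.2 and 8.3.4 say otherwise.
- **That harms cannot be compared between the arms without bias.** The complications comparison is unfiltered, and a filter applied equally costs power without creating a difference.

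A third tempting inference is that the classifiers are unblinded. Section 4.1 names the anesthesiologist or surgeon without saying which, 6.3 states double blinding, and 8.3.3.2 names the PI and attendings. Overlap is possible but not shown.

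Nor is it established that saline-arm harms go unreported, since the synopsis wording would include them. A classifier unaware of the arm could not exclude them on that ground anyway; the exclusion could operate only once the allocation is known.

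It can also be said that expecting no adverse events is loose wording beside risks described as minimal or below 1%, and that the block may well be standard care for surgeons who use it in every case (2.2). Both are fair. They do not cover the saline injection, which is given only because of the trial.

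The reply does not remove the contradiction. Section 8.2 gives no form, window or grading, and the patient worksheet collects only pain scores and analgesic use. Section 8.3.4 is headed as a time period and states none. Complications are undefined, so it is unclear whether 9.4.9 would cover local anesthetic toxicity.

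**Conclusion.** The point holds in this form. Adverse event status and IRB reporting depend on attribution to the intervention, in conflict with 8.2, 8.3.3.2 and 8.3.4. If the definition is followed, events judged unrelated drop out of both, and saline-injection harms may do so as well.

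An adverse event table built on the definition would lose sensitivity: power roughly halves if half the events are counted in each arm. Bias is conditional. With no true difference, false positives run from 6% to 76% over attribution splits from 0.6 / 0.4 to 0.8 / 0.2 and event rates from 10% to 30%. These are assumed values that show the mechanism; they do not predict what will happen in this trial. The plan does not establish that attribution will differ by arm, and it would be wrong to read it as making every harms comparison biased.

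The defect should be corrected because the stated rule gives poorer safety reporting when followed. It does not affect the primary analysis of pain scores.

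**What to change.** - **8.3.1 and 8.3.2:** define an adverse event, and a serious one, as any untoward medical event in either arm from the block to the two-week visit, whatever its cause.
- **8.3.3.2 and 8.3.4:** record every event first. Enter relatedness afterwards as a separate field, judged by a team member unaware of the allocation where one is available. The key roles section was not in the text reviewed, so availability could not be checked.
- **8.3.5 and 8.3.6:** align IRB reporting with the new definition.
- **6.1.1 and synopsis:** use one description of the intervention, so that the status of saline-injection harms is settled.
- **9.4.4:** replace N/A with all events and related events by arm as treated.
- **9.4.9:** define complications and state how they relate to adverse events.
- **2.3.1, 2.3.3, 8.3.1 and 8.3.2:** reconcile the statement that no adverse events are expected with the listed risks, and say in 2.3.3 that the saline injection is a study procedure.

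The cost is protocol wording and slightly more event recording at a visit that already takes place.
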